Spinal excitability measurements: <= 25 single PNS pulses to the left wrist at <= 120% of M-max. Measurements will be taken immediately before PCMS and at 0, 20 and 40 minutes after PCMS.

Voluntary motor output measurements: <= 5 maximum voluntary contractions of the FDI, each lasting <= 5 seconds. Measurements will be taken immediately before PCMS and at 0, 20 and 40 minutes after PCMS. Manual dexterity measurements. <= 5 attempts of the 9-hole peg test. Measurements will be taken immediately before PCMS and at 0, 20 and 40 minutes after PCMS.

5 Data Analysis

Describe the data analysis plan, including any statistical procedures or power analysis. To input text, click in the light grey area below.

Experiment 1:

- 1. Primary outcome: Amplitude of MEPs evoked during brain states reflecting strong, weak, and/or random corticospinal tract recruitment
 - a. This outcome will be evaluated using linear-mixed effects models (fixed effect of state, random effect of subject) with alpha equal to 0.05.

Experiment 2:

- 1. Primary outcome: amplitude of FDI muscle response after TST application during brain states reflecting strong, weak, and random corticospinal tract recruitment.
- 2. Secondary outcome: area under the curve of FDI muscle response after TST application during brain states reflecting strong, weak, and random corticospinal tract recruitment.
 - a. Both outcomes will be evaluated using linear mixed-effects models (fixed effect of state, random intercept of subject) with alpha equal to 0.05.

Experiment 3:

- 1. Primary outcomes: Maximum FDI force output, FDI activation (calculated using the root-mean-square of EMG signals obtained during FDI contractions)
- 2. Secondary outcome: Number of pegs placed per attempt at the 9-hole Pegboard test.
- 3. Exploratory outcomes: Amplitudes of MEPs produced by scalp TMS, amplitudes and persistence of Fwaves evoked by wrist PNS
 - All outcomes will be evaluated before and after PCMS. Outcomes will be analyzed using linearmixed effects models (fixed effects of condition and time point, random intercept of subject).
 Main effects will be evaluated using likelihood ratio tests, and p-values from post-hoc contrasts will be corrected for multiple comparisons. Alpha will be equal to 0.05.

STUDY ELEMENT IDENTIFICATION

6 Study Elements

Click on the check box (or double click and type an "X" if using Google Docs) each procedure included in your study.

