- current or recent (within the last 3 months) use of medications acting on the central nervous system, including but not limited to: antipsychotic drugs, antidepressants, benzodiazepines, prescription stimulants

f Additional Population Information

To input text, click in the light grey area below. none

14 Total Sample Size

To input text, click in the light grey area below. Experiment 1: target N=20, maximum N=30 Experiment 2: target N=20, maximum N=30 Experiment 3: target N=20, maximum N=30

Maximum N values are increased compared to the target N to account for subject drop-out and withdrawal. Participants may participate once in each experiment.

15 Sample size rationale

To input text, click in the light grey area below.

Experiments 1 and 2: Previous work examining brain state-dependency of corticospinal transmission achieved adequate power with N=17 ([name] et al. 2019; [name] and Quentin 2021) and N=12 (Zrenner et al. 2018). The expected effect sizes of Experiments 1 and 2 are predicted to be very similar to that observed in these two studies. To be conservative in our effect size estimates, we have increased the sample size from N=12-17 to N=20 to ensure adequate power.

Experiment 3: Previous work examining PCMS in healthy adults identified a significant effect of this intervention with N=14 (Bunday and Perez 2012). More recent work examining the impact of voluntary contraction of PCMS efficacy identified significant enhancement of PCMS efficacy with N=14. The expected effect size in Experiment 2 is predicted to be very similar to that observed in these two studies. To be conservative in our effect size estimates, we have increased the sample size from N=14 to N=20. A maximum of N=30 will be recruited to account for subject withdrawal.

SCREENING AND RECRUITMENT

16 Identification and Screening

Click on the check box (or double click and type an "X" if using Google Docs) if true.

This study involves obtaining information or biospecimens for the purpose of screening, recruiting or determining eligibility of prospective subjects prior to informed consent by either:

1. Oral or written communication with the prospective subject or LAR

2. By accessing records containing identifiable private information or stored identifiable biospecimens.

17 Identification and/or Screening Procedures

Describe the identification and/or screening procedures below. To input text, click in the light grey area below.

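### Experiment 3 collects a pre-PCMS value of each primary outcome in every session but does not use it for baseline adjustment; a post-minus-pre contrast would give up some power at N=20

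*Combined protocol and SAP*

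**What the plan says.** Section 5, Experiment 3, names two primary outcomes: "Primary outcomes: Maximum FDI force output, FDI activation (calculated using the root-mean-square of EMG signals obtained during FDI contractions"). Section 4 (Voluntary motor output measurements) gives the schedule: "Measurements will be taken immediately before PCMS and at 0, 20 and 40 minutes after PCMS". Section 11 lists the pre-PCMS measurements among the steps for Days 1-4, so each session has its own baseline, taken before that session's intervention.

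On the analysis, section 5 says "All outcomes will be evaluated before and after PCMS", and then "Outcomes will be analyzed using linearmixed effects models (fixed effects of condition and time point, random intercept of subject"). Main effects are tested by likelihood ratio, post-hoc contrasts are corrected for multiplicity, and "Alpha will be equal to 0.05". The contrasts are not named. No baseline covariate, change score, equal-baseline constraint, condition-by-time term or session-level effect appears.

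Section 14 gives "Experiment 3: target N=20, maximum N=30". Section 15 supports the target by reference to earlier studies: "To be conservative in our effect size estimates, we have increased the sample size from N=14 to N=20".

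**The concern.** Hypothesis 3 is about PCMS increasing force and activation more in strong brain states than in weak or random ones. To test that within the stated model framework, one would add a condition-by-time contrast. If each condition has its own freely estimated pre-PCMS mean, and the data are complete, that contrast is post minus pre. It therefore subtracts the whole error of one pre-PCMS assessment from each session's post-PCMS result.

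The design offers something better. The pre-PCMS value precedes that session's intervention and condition order is counterbalanced. If earlier sessions leave no residual effect, the expected pre-PCMS mean is the same in every condition. A model that uses this fact subtracts only the predictive part of the baseline. At stake is power for the strong-versus-weak and strong-versus-random contrasts on both primary outcomes. The target is 20 participants, the contrasts are corrected for multiplicity, and participants may complete fewer than four conditions, so a given pairwise contrast may rest on fewer than 20 pairs.

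**Working it through.** **The plan's own figure.** N=20 cannot be reproduced. It is raised from N=14 with no effect size, standard deviation, power or correlation. The sentence on effect size in the Experiment 3 rationale also names another experiment ("The expected effect size in Experiment 2 is predicted to be very similar to that observed in these two studies"), which should be reconciled. As a benchmark only, a paired t test at two-sided 0.05 (sidedness is not stated, so two-sided is assumed) with 20 pairs and 80% power needs a noncentrality of 2.95, a standardised paired difference of 2.95/√20 = 0.66.

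**Inputs.** From the documents: one pre-PCMS and three post-PCMS measurements per session, 20 participants, alpha 0.05. Assumed: the change contrast has 80% power at N=20; within-session variance is scaled to 1 after removing the subject effect; one common correlation rho links all measurements in a session. Rho is varied because the documents give no value.

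**Formulas.** With k post-PCMS points averaged:

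- Var(post mean) = rho + (1 − rho)/k, and Cov(pre, post mean) = rho.
- Change variance = Var(post mean) + 1 − 2·rho.
- Adjusted variance = Var(post mean) − rho².
- The difference is (1 − rho)², which is positive for every rho below 1.

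A contrast between two conditions doubles both variances, so the ratio is unchanged. Power after adjustment uses noncentrality 2.95/√ratio with one degree of freedom deducted.

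Example, rho = 0.5 and k = 3: Var(post mean) = 0.5 + 0.5/3 = 0.667; change = 0.667 + 1 − 1 = 0.667; adjusted = 0.667 − 0.25 = 0.417; ratio = 0.625; noncentrality 2.95/√0.625 = 3.73; power about 94%.

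| rho | change, k=3 | adjusted, k=3 | ratio, k=3 | power, k=3 | ratio, k=1 | power, k=1 |
|---|---|---|---|---|---|---|
| 0.2 | 1.067 | 0.427 | 0.40 | 99% | 0.60 | 95% |
| 0.5 | 0.667 | 0.417 | 0.625 | 94% | 0.75 | 90% |
| 0.8 | 0.267 | 0.227 | 0.85 | 86% | 0.90 | 84% |
| 0.9 | 0.133 | 0.123 | 0.925 | 83% | 0.95 | 82% |
| 0.95 | 0.067 | 0.064 | 0.962 | 81% | 0.975 | 81% |

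At rho 0.85 with three post-PCMS points, power is 84.2%. The gain is therefore under 5 points at high rho whether one or three post-PCMS points are used.

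**Simulation check of power** (20 participants, 4 conditions, one pre and three post, one post-PCMS summary per session). At rho 0.3, 0.5, 0.8 and 0.9 the change contrast had 79-80% power and the adjusted contrast 98%, 93%, 85% and 82%. Type I error was about 5% for both.

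**Simulation check of the covariate in the plan's random structure.** With three post-PCMS rows per session, the covariate added and subject effects only, type I error for one pairwise contrast at nominal 5% was about 10%, 14%, 18% and 18% at rho 0.2, 0.5, 0.8 and 0.9. The three rows from one session share a session deviation that the subject intercept does not absorb. With one summary per session, type I error was about 4-6%.

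**The case against.** The strongest reply is that this compares two analyses, neither of which is in the plan. Section 5 tests main effects and contains no change contrast. Its condition main effect averages pre with post and does not subtract the baseline at all. That is correct: a reader might infer that the plan specifies a wasteful change-score test, and the documents do not support that. The missing condition-by-time contrast and session effect are larger problems. Repairing both with free pre-PCMS means would still leave this loss in place, so the point survives in conditional form.

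Second, rho may be high. Each assessment is up to five maximum contractions, which can reduce its error. Sessions are on separate days, and section 11 allows skin marking to keep electrode positions consistent, which acknowledges between-session variation. Both push rho upward, where the gain shrinks to 1-3 points. This stands as a limit on size. The documents do not establish rho in either direction.

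Third, a post-minus-pre contrast does not need equal expected baselines, whereas adjustment does. Sessions need be only 24 hours apart and participants may complete one to four conditions, so achieved order balance is not guaranteed. This also stands, and it is why the change score should be kept as a sensitivity analysis.

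Two further inferences should be resisted. Keeping the pre-PCMS value as a response row is not wasteful in itself: with equal pre-PCMS means and a session effect it recovers the same information. Nor does the point show that Experiment 3 is underpowered, since the documents give no effect size or variance from which to judge that.

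**Conclusion.** The point holds as an efficiency improvement at almost no cost. The adjusted variance is below the change-score variance at every rho under 1, before the small cost of estimating the slope. From an 80% starting point the gain runs from about 19 points (rho 0.2, three post-PCMS points) to about 1 point (rho 0.95), and no single figure should be quoted without its rho. The figures assume a common within-session correlation, complete data on 20 participants, a two-sided 5% test before multiplicity correction, and no carryover between sessions. That the pre-PCMS value is a level of time point is the natural reading of section 5, not an explicit statement. A reader might also infer that leaving out the adjustment biases the comparison. It does not: with equal expected baselines the change-score and adjusted contrasts both estimate the same effect, and only their precision differs.

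**What to change.** In section 5, Experiment 3, analyse the post-PCMS values with that session's pre-PCMS value of the same outcome as a covariate, split into the participant's mean pre-PCMS value and the session's deviation from it. In the same edit, either add a random participant-by-session effect or analyse one post-PCMS summary per session. The covariate must not be added to a model with only a subject intercept.

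An equivalent option is to keep the pre-PCMS rows, constrain the pre-PCMS mean to be equal across conditions, and include a condition-by-time term and a participant-by-session effect.

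Apply this to both primary outcomes, and in the same way to the secondary and exploratory outcomes. Keep the change-score contrast as a sensitivity analysis, and compare the pre-PCMS means across conditions as a check on carryover.

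The cost is a few sentences, one or two model degrees of freedom, and reliance on equal expected pre-PCMS means. No new data, sessions or participants are needed.

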hand muscle activation, (c) voluntary hand muscle force production, and (d) hand dexterity more than identical PCMS applied during brain states reflecting weak corticospinal tract recruitment or random brain states.

3 Study Background

To input text, click in the light grey area below.

Stroke is the leading cause of long-term disability in the United States (Go et al. 2013) and commonly disrupts the corticospinal tract (Twitchell 1951). The presence of residual corticospinal connections is one of the best prognostic markers of post-stroke motor function and recovery potential (Stinear et al. 2007), indicating that the most serious and long-lasting stroke-related motor deficits are caused by corticospinal tract disruption. Interventions capable of strengthening residual corticospinal connections are thus promising candidates for improving motor function after stroke. Paired cortico-motoneuronal stimulation (PCMS) can strengthen corticospinal connections in healthy adults (Taylor and Martin 2009; Bunday and Perez 2012) and patients with corticospinal tract disruption caused by spinal cord injury (Bunday and Perez 2012). PCMS involves repeatedly delivering precisely-timed pairs of non-invasive peripheral stimuli (via transcutaneous peripheral nerve stimulation) and cortical stimuli (via transcranial magnetic stimulation) such that they induce long-term potentiation via spike-timing dependent plasticity (STDP_{LTP}) at corticospinal-motoneuronal synapses, which are essential to human dexterity (Lemon 2008).

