Real-time EEG analysis: The EEG system will stream data in real-time to a dedicated computer. This computer will analyze the data in real time to identify brain states associated with strong or weak corticospinal tract recruitment (see above), or a random mixture of the two. When desired states are identified, either a single TMS pulse (see *Evaluation of state-targeting* accuracy) or the TST (see *TST assessment*) will be triggered. *Evaluation of state-targeting accuracy:* <= 150 single TMS pulses will be applied to the scalp at <= 120% of scalp RMT during EEG recordings.

Calculation of ISIs for TST assessment: The following stimulation procedures will be performed to calculate the ISIs for TST assessment.

- 1. <= 25 Single-pulse TMS to the scalp at <= 120% of scalp RMT
- 2. <= 25 Single-pulse PNS to the left wrist at <= 120% of M-max
- 3. <= 25 Single-pulse PNS to the left Erb's point at <= 120% of M-max

TST assessment: The TST will be applied according to an established protocol (Magistris et al. 1998) using consecutive application of TMS (<= 120% of scalp RMT), PNS at the left wrist (<= 120% of M-max), and PNS at the left Erb's point (<= 120% of M-max). The delays between each stimulus will be individualized based on each participants central and peripheral conduction times (see *Calculation of ISIs for TST assessment*). The TMS portion of the TST will be timed to occur during brain states reflecting strong corticospinal tract recruitment, weak corticospinal tract recruitment, or random brain states, using real-time EEG analysis. <= 50 TST applications will be performed per brain state condition.

Experiment 3

Design: within-subjects, single group Population: healthy adults (≥ 18 years old)

Conditions: At least 24 hours will elapse between sessions.

- 1. Active PCMS delivered during brain states reflecting strong corticospinal recruitment
- 2. Active PCMS delivered during brain states reflecting weak corticospinal recruitment
- 3. Active PCMS delivered during random brain states

- 4. Control PCMS delivered during brain states reflecting strong corticospinal recruitment
 - a. The order of conditions will be counterbalanced
 - b. Participants may complete one, two, three or four of the conditions

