- The TST will be applied during brain states reflecting strong corticospinal recruitment, brain states reflecting weak corticospinal recruitment, and randomly selected brain states according to an established procedure (Magistris et al. 1998), with details below. EMG data will be recorded and processed offline to calculate the primary and secondary outcomes. EEG data will be recorded and processed offline to ensure accurate state identification as a quality control procedure (Zrenner et al. 2018; [name] et al. 2020).
 - TMS will be timed using the real-time EEG analysis algorithm
 - After an interstimulus interval equal to delay 1, Wrist PNS will be applied.
 - After an interstimulus interval equal to delay 2, Erb's point PNS will be applied.
- The EEG cap, EMG electrodes, and PNS electrodes will be removed and participants will leave the laboratory.
- If participants are asked to complete two sessions, the same experimental procedures described above may be used during the second session. The second session may be used to evaluate between-day reliability of the measurements made during the first session. At least 24 hours will elapse between sessions.

Experiment 3

Days 1-4 (at least 24 hours will elapse between sessions)

- The participant and research team member will review and discuss the informed consent document.
- Eligibility will be formally determined by the research team member by reviewing a list of the inclusion and exclusion criteria verbally with the participant (see attachments).
- Participants will complete a short demographics survey.
- The skin on the left hand and wrist will be cleaned using isopropyl alcohol. EMG electrodes will be attached to a maximum of 5 hand and wrist muscles using medical grade adhesive. PNS electrodes will be attached to the left wrist using medical grade adhesive. A ground electrode will also attached to the dorsum of the hand in the same manner.
- The scalp TMS hotspot will be determined as the site of the scalp producing the most reliable focal muscle twitch within the left first dorsal interosseous muscle. The scalp RMT will be determined using an automatic threshold tracking tool (Awiszus and Borckhardt 2011) as the minimum stimulation intensity needed to elicit a MEP of 50 microvolts in peak-to-peak amplitude in response to 50% of stimuli. EMG signals may be recorded for offline quality control analysis.

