- Single-pulse TMS pulses will be delivered during EEG and EMG recordings. Immediately afterwards, EEG and EMG data will be analyzed using machine learning. The brain states identified using machine learning will be used for subsequent real-time EEG analysis.
- The M-max following PNS at the wrist will be determined by increasing stimulation intensity until a larger response cannot be obtained. EMG signals may be recorded for offline quality control analysis.
- Electrode positions may be marked on the skin using a skin-safe surgical marker to ensure consistent electrode placement across sessions.
- Single-pulse TMS to the scalp and wrist PNS will be performed to calculate delays needed for PCMS (see Design and Methodology). EMG signals will be recorded to enable delay calculation.
- Delays for PCMS application will be calculated using the following formulas (units are milliseconds; Bunday and Perez 2012; Urbin et al. 2021):
 - Peripheral Conduction Time (PCT) = (F-wave latency –M-wave latency) * 0.5
 - Central Conduction Time (CCT) = MEP latency (PCT + M-wave latency)
 - Active PCMS Delay = (PCT CCT) X ms (where X = 1 5 ms)
 - \circ Control PCMS Delay = (PCT CCT) + X ms (where X = 5 30 ms)
- The real-time EEG analysis algorithm will be used to deliver TMS pulses during the target brain state for that session. The order of brain states targeted per session will be counterbalanced across subjects. During this time, participants will rest quietly with their eyes open (Zrenner et al. 2018; [name] et al. 2020). EEG and EMG data will be recorded for offline quality control analysis.

- Participants will complete pre-PCMS measurements of corticospinal excitability, spinal excitability, voluntary motor output, and manual dexterity (see Design and Methodology). EMG signals will be recorded during all measurements and processed offline to obtain outcome measures. EEG may recorded for offline quality control analysis.
- The PCMS intervention will be delivered (see Design and Methodology) during the target brain state for that session. The order of brain states targeted per session will be counterbalanced across subjects. EEG and EMG signals will be recorded for subsequent quality control analysis.
 - Active PCMS during brain states reflecting strong corticospinal recruitment, with the delay between scalp TMS and wrist PNS equal to the Active PCMS delay.

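### Experiment 3: the planned model tests a condition main effect, not a difference in gain, and leaves session-to-session variation out of its error term

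*Combined protocol and SAP*

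**What the plan says.** Section 2, Hypothesis 3, predicts that strong-state PCMS will increase four outcomes, ending with "hand dexterity more than identical PCMS applied during brain states reflecting weak corticospinal tract recruitment or random brain states". In section 4 (Experiment 3), each outcome follows the same schedule within a session: "Measurements will be taken immediately before PCMS and at 0, 20 and 40 minutes after PCMS".

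Section 5 (Data Analysis, Experiment 3) makes maximum force and EMG activation of the first dorsal interosseous (FDI) the primary outcomes. The model for all outcomes has "fixed effects of condition and time point, random intercept of subject". The testing rule is "Main effects will be evaluated using likelihood ratio tests, and p-values from post-hoc contrasts will be corrected for multiple comparisons", with alpha 0.05. The post-hoc contrasts are not named.

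One brain state is targeted per session, and sessions are at least 24 hours apart. Section 11 adds: "The order of brain states targeted per session will be counterbalanced across subjects". Electrodes are attached at the start of each session and removed at the end. Section 4 also allows incomplete sets: "Participants may complete one, two, three or four of the conditions".

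**The concern.** There are two separate problems.

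**The quantity tested.** The hypothesis is a difference between conditions in pre-to-post change. An additive model in condition and time point has one condition difference, the same at every time point, including before any PCMS has been given. The pre-PCMS value is collected in every session but is treated as one more outcome value, not as a baseline.

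**The error term.** The four values from one session share whatever is particular to that day. Within a participant, session coincides with condition, so this shared variation sits inside every condition difference. A subject intercept cannot absorb it. Counterbalancing stops it favouring one condition on average but does not put it into the standard error.

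These are the only planned tests of the two primary outcomes of Experiment 3. A significant condition effect could reflect day-to-day variation, and it would not by itself show a larger gain.

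**Working it through.** **Inputs from the documents.** Target N = 20 (section 14); four conditions and four time points, one before and three after PCMS (section 4); the model, test and alpha of 0.05 (section 5). Section 15 argues N = 20 from earlier studies with N = 14 and gives no effect size, SD or power, so there is no planned figure to reproduce.

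**Assumptions.** Session variance is 0, 20, 50 or 80% of within-person variance; tests are two-sided. For power, the strong-state condition alone has an advantage d = 0.5 within-person SD at all three post times.

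**Step 1: what the condition effect estimates.** Let the strong-state session start at a baseline difference b, carried through the session, and gain d at each post time. With balanced data the estimate is [b + 3(b + d)]/4 = b + 0.75d. With b = 0 and d = 0.5 this is 0.375 (simulated 0.373 to 0.376). The model cannot separate b from d.

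**Step 2: standard error of a two-condition difference.** Take residual SD 1 and session SD s.
- True SE = √[2(s² + 1/4)/20].
- The subject-only model pools 3 between-session and 12 within-session degrees of freedom per participant: variance [3(1 + 4s²) + 12]/15 = 1 + 0.8s², so model SE = √[2(1 + 0.8s²)/(4 × 20)].
- Actual error of a nominal 5% contrast = 2[1 − Φ(1.96 ÷ SE ratio)].

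| s | Session share s²/(1 + s²) | True SE | Model SE | Ratio | Actual error |
|---|---|---|---|---|---|
| 0 | 0% | 0.158 | 0.158 | 1.00 | 5.0% |
| 0.25 | 6% | 0.177 | 0.162 | 1.09 | 7.2% |
| 0.5 | 20% | 0.224 | 0.173 | 1.29 | 12.9% |
| 1.0 | 50% | 0.354 | 0.212 | 1.67 | 24% |

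**Step 3: simulation of the planned test and alternatives.** Each trial has 20 participants × 4 conditions × 4 times. The planned test is the maximum-likelihood ratio test of condition on 3 df. Its closed form for balanced data agreed with a standard mixed-model fit. There were 8,000 trials per setting, except 1,500 for the baseline-adjusted model, 300 for incomplete sets and 20,000 for the added-interaction row.

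| Session share | 0% | 20% | 50% | 80% |
|---|---|---|---|---|
| **False positives (nominal 5%)** | | | | |
| Planned likelihood ratio test | 5.6 | 20.7 | 43.4 | 60.9 |
| Strong-vs-weak contrast, planned model | 5.0 | 13.3 | 24.0 | 34.7 |
| Planned test, random 1–4 conditions each | not run | 22.3 | 49.0 | 67.0 |
| Interaction added, subject intercept only | 6.2 | 2.3 | 0.1 | 0.0 |
| **Power, strong-vs-weak** | | | | |
| Main effect, valid session error term | 64.4 | 44.8 | 31.5 | 24.6 |
| Gain contrast (mean post minus pre) | 27.8 | 31.4 | 48.2 | 85.0 |
| Baseline-adjusted post values | 75.8 | 58.2 | 60.9 | 89.3 |
| Baseline-adjusted, alpha 0.025 | 64.8 | 45.5 | 49.0 | 82.3 |

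At a 6% session share the planned test rejects in 9.0% of 10,000 null trials. Under the null, the main effect with a session error term rejects in 4.9 to 5.1% of trials and the baseline-adjusted model in 4.7 to 5.5% (4.9 to 6.3% with incomplete sets). The baseline-adjusted estimate is 0.49 to 0.50 for a true 0.5.

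**Step 4: repeated contractions.** Section 4 allows up to five contractions per time point and does not say whether they are averaged. If five enter as separate rows, the planned test's error is 31, 67 and 89% at s = 0.25, 0.5 and 1.0.

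**The case against.** The strongest reply is that this is a short paragraph in an ethics-board form. It does not exclude an interaction, and the unnamed post-hoc contrasts may be gain contrasts. That stands as a point about reading: the excess false positives belong to the additive model as written. It does not rescue the plan. With an interaction added and the subject-only intercept kept, the interaction test errs the other way (6.2 / 2.3 / 0.1 / 0.0%) and loses power. The session term or baseline adjustment is needed on either reading.

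Several other objections have some force:
- **Session variance is unknown.** With none, the planned test is close to nominal. The 80% setting is an extreme and should not carry the argument.
- **The sources of session variance differ by outcome.** Re-determining the TMS threshold bears on evoked potentials, which are exploratory, and not on force. Electrode placement bears on EMG activation, and the protocol offers some mitigation: "Electrode positions may be marked on the skin using a skin-safe surgical marker to ensure consistent electrode placement across sessions". That step is optional and shows that placement is expected to vary. Day-to-day variation in force is plausible but not documented.
- **A diluted estimate is not lower power.** At 0 and 20% session share a valid main-effect test is more powerful than a raw gain contrast (64 and 45% against 28 and 31%). This is why baseline adjustment is preferred below. The factor 0.75 also assumes a constant gain over the three post times.
- **The incomplete-set runs are small.** They use 300 trials each and an assumed 1–4 distribution. Extra sessions after technical difficulties mean that session and condition need not always coincide exactly.

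**Conclusion.** The concern holds. As written, the analysis does not test Hypothesis 3. This follows from the model's form and needs no variance assumption: the additive condition effect is the same before and after PCMS, takes in any baseline difference, and recovers 75% of a constant gain difference.

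The false-positive result is conditional on the additive reading and on some variation between sessions. Under those conditions the planned test exceeds 5%: about 9% at a 6% session share, 21% at 20% and 43% at 50%, with n = 20 and one value per time point. The documents give no variances, so this is a range and not an estimate for this trial. Because the test concerns both primary outcomes, the paragraph should be corrected before the data are analysed.

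**What to change.** Rewrite the Experiment 3 paragraph in section 5 as follows.
- **Model:** post-PCMS values at 0, 20 and 40 minutes, with that session's pre-PCMS value as covariate; fixed effects of condition, time point and condition-by-time; random effects for subject and subject-by-session.
- **Primary tests:** strong-vs-weak and strong-vs-random active PCMS, each averaged over the three post times, with the multiplicity correction already planned.
- **Acceptable alternative:** keep all four time points with condition-by-time and the subject-by-session random effect. Test the same two contrasts as prespecified differences in gain (mean post minus pre), not through the omnibus interaction. This isolates the gain but has less power unless session variance is substantial.
- **Remove** the main-effect likelihood ratio tests as the basis for the Hypothesis 3 claim. If an interaction or gain contrast was always intended, write it in, together with the session term.
- **State** how repeated contractions at a time point are reduced to one value.

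The cost is the wording of one paragraph, with no new data, visits or participants. It does not settle whether N = 20 is enough: at d = 0.5 and alpha 0.025 per contrast, the recommended model has about 65 / 46 / 49 / 82% power at the four session shares.
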